8.2.2 Cohort B

For powering purposes, the combined Cohort B will be given the same weight as the primary dosing cohort (Cohort A). Thus, Cohort B will enroll 75 subjects to achieve 60 completers. Each of the 5 dosing groups within Cohort B will enroll 15 subjects each to achieve 12 completers.

8.3 Primary Efficacy Evaluation

The primary endpoint for this study is the change from baseline in HbA1C at Visit 9 (Part 2 Week 10). Randomization occurs at Visit 3 (Part 1 Week 0), during which subjects will be stratified by Screening HbA1C values and current treatment regimen.

8.3.1 HbA1C Evaluation

Mean change from baseline to Week 12 HbA1C (Visit 9 value – Visit 3 value) will be tested using an analysis of covariance (ANCOVA) model using baseline HbA1C and whether the subject is using additional antidiabetes drugs (beyond metformin) as covariates.

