- d. Use of medications known to modify glucose metabolism or to decrease the ability to recover from hypoglycemia such as oral, parenteral, and inhaled steroids (as discussed above), and immunosuppressive or immunomodulating agents.
- 13. Known allergy to soy.
- 14. Subject is on a weight loss program and is not in the maintenance phase, or subject has started weight loss medication (e.g., orlistat or liraglutide), within 8 weeks prior to Screening.
- 15. Subject has had bariatric surgery.
- 16. Subject is pregnant or breast-feeding.
- 17. Subject is a user of recreational or illicit drugs or has had a recent history (within 1 year of Screening) of drug or alcohol abuse or dependence. (Note: Alcohol abuse includes heavy alcohol intake as defined by >3 drinks per day or >14 drinks per week, or binge drinking) at Screening. Occasional intermittent use of cannabinoid products will be allowed provided that no cannabinoid products have been used during the 1 week prior to each visit.
- 18. One or more contraindications to metformin as per local label.
- 19. History of gastrointestinal disorders (e.g. hypochlorhydria) with the potential to interfere with drug absorption.
- 20. At the Principal Investigator's discretion, any condition or other factor that is deemed unsuitable for subject enrollment into the study.

Statistical Methods

The primary endpoint for this study is the change from baseline in HbA1C at Visit 9 (Part 2 Week 10). Mean change from baseline to Week 12 HbA1C (Visit 9 value – Visit 3 value) will be tested using an analysis of covariance (ANCOVA) model using baseline HbA1c and whether the subject is using additional antidiabetes drugs (beyond Metformin) as covariates.

Observed means and mean changes from baseline for HbA1C and FPG will be analyzed by visit using a method similar to the primary endpoint.

Change from baseline to Week 12 (Visit 9, Part 2 Week 10) in PPG parameters during a MMTT, including AUC₀₋₆₀, AUC₀₋₁₂₀, and 1 & 2-hour PPG absolute levels and excursions will be analyzed using a method similar to the primary endpoint.

Changes from baseline to Week 12 (Visit 9, Part 2 Week 10) in mean 24-hour, mean day time (6 AM to 10 PM) and mean night time (10 PM to 6 AM) glucose as measured by CGM will be analyzed using a method similar to the primary endpoint. For a day to be included in the calculations of the overall means, the subject must have at least 80% of the expected glucose readings.

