4 STUDY SUBJECT SELECTION

4.1 Inclusion Criteria

Each subject must meet all of the following criteria to be eligible for the study:

- 1. Male and female subjects aged 18 and older.
- 2. Established diagnosis of T2DM for at least 6 months prior to Screening, with an HbA1C ≥ 7.5%.
- 3. Stable dose of metformin (at least 1500 mg or maximal tolerated dose)/oral antidiabetic (OAD) for a period of at least 3 months prior to Screening.
- 4. Taking metformin only or metformin in addition to no more than two of the following: SU, DPP-4, SGLT-2, or TZD.
- 5. Body mass index (BMI) of up to 40 kg/m² at Screening and stable weight, with no more than 5 kg gain or loss in the 3 months prior to Screening.
- 6. Renal function eGFR $> 30 \text{ ml/min/}1.73 \text{ m}^2$
- 7. Females of childbearing potential must have a negative serum pregnancy test result at Screening.
- 8. Females who are not of childbearing potential are defined as:
 - a. post-menopausal (defined as at least 12 months with no menses in women ≥45 years of age) or
 - b. has had a hysterectomy and/or bilateral oophorectomy, or had bilateral tubal ligation or occlusion at least 6 weeks prior to Screening
- 9. Subjects who are of childbearing potential must:
 - a. agree to remain abstinent from heterosexual activity[†] or agree to use (or have their partner use) acceptable contraception to prevent pregnancy within the projected duration of the trial and for 14 days after the last dose of blinded investigational product. Two methods of contraception will be used to avoid pregnancy. Acceptable combinations of methods include:
 - i. Use of one of the following double-barrier methods: diaphragm with spermicide and a condom; cervical cap and a condom; or a contraceptive sponge and condom
 - ii. Use of hormonal contraception (any registered and marketed contraceptive agent that contains an estrogen and/or a progestational agent [including oral, subcutaneous, intrauterine and intramuscular agents, and cutaneous patch]) with one of the following: diaphragm with spermicide; cervical cap; contraceptive sponge; condom; vasectomy; or IUD.
 - iii. Use of an IUD with one of the following: condom; diaphragm with spermicide; contraceptive sponge; vasectomy; or hormonal contraception (see above).
 - iv. Vasectomy with one of the following: diaphragm with spermicide; cervical cap; contraceptive sponge; condom; IUD; or hormonal contraception (see above).

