5.2 Randomization

Of the total 360 subjects, 265 subjects will be randomized to Cohort A and receive ORMD-0801 or placebo in one of 3 treatment regimens: QHS, BID, or TID. The actual treatment (ORMD-0801 or placebo) will be double-blinded to the subjects, investigators, monitors, and staff members responsible for treating and evaluating subjects, but the treatment regimen will be unblinded.

Creation, maintenance, and communication of the randomization scheme will be managed by an interactive web-based response system (IWRS). Subjects will be randomized 1:1:1 to QHS, BID, or TID and 1:3 (placebo:ORMD-0801) within each of those regimens at Visit 3. Therefore the overall randomization will be 1:1:1:1 (all placebo dosing regimens combined: ORMD-0801 QHS: ORMD-0801 BID: ORMD-0801 TID). Randomization will be in block sizes of 12 (1:3;1:3;1:3 [placebo QHS: ORMD-0801 QHS; placebo BID: ORMD-0801 BID; placebo TID: ORMD-0801 TID]).

An additional 75 subjects will be randomized to Cohort B and receive one of 5 treatment regimens (1:1:1:1): excipient matched placebo QHS, ORMD-0801 8 mg QHS, ORMD-0801 8 mg BID, ORMD-0801 16 mg QHS, or ORMD-0801 16 mg BID. Randomization will be in block sizes of 5 (1:1:1:1:1 [excipient matched placebo QHS: ORMD-0801 8 mg QHS: ORMD-0801 8 mg BID: ORMD-0801 16 mg QHS: ORMD-0801 16 mg BID]).

The randomization will be centralized and stratified by a) Sulfonylurea usage and b) whether they are on metformin alone or metformin plus one or 2 additional oral antidiabetic drugs at Screening. This will help ensure balanced treatment distribution of the subjects across the strata.

The additional 20 subjects in Cohort A who will receive excipient-matched placebo will not be randomized.

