8.1 Study Design

The primary analysis is a comparison of change in HbA1c for the ORMD-0801 treated groups and placebo. Let pC be the delta HbA1C for the control (placebo) arm and let pT be the delta HbA1C for the treatment (ORMD-0801) arms. The primary analysis is:

H0: pC=pT

H1: pC < pT

Trial success is defined as rejecting the null hypothesis of no difference in delta HbA1C between active study drug and placebo.

In order to preserve on overall alpha level of 0.05, a stepwise approach will be used for hypothesis testing. The initial hypothesis will be ORMD-0801 TID versus combined placebo. If the initial hypothesis results in a rejection of H0, the secondary test, ORMD-0801 BID versus combined placebo, will take place. If both the initial and secondary hypotheses result in rejections of H0, the third test, ORMD-0801 QHS versus combined placebo will take place.

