8.2 Sample Size

8.2.1 Cohort A

The primary efficacy endpoint is the change from baseline in HbA1C at Visit 9 (Part 2- Week 10) after 12 weeks of active treatment. Based on previous results, a drop in HbA1C of 0.6% is expected with a standard deviation of 1.2. The primary analysis is based on combining the BID and TID treatment regimens together to compare to combined placebo. In order to achieve 80% power, there 48 completers are needed per treatment group.

Assuming an approximate 20% drop out rate, 240 randomized subjects would yield around 192 completers or approximately 48 subjects per treatment group. This would provide 80% power to detect a decrease in HbA1C of 0.6% for the BID and TID active combined versus combined placebo.

An additional 20 non-randomized subjects will be enrolled to receive excipient matched placebo to ensure that the fish oil placebo does not have a significant effect on efficacy or safety. The choice of adding 20 subjects is not based on statistical considerations.

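### Sections 5.2 and 8.3 name different randomisation strata, and the primary ANCOVA omits sulfonylurea use although 5.2 stratifies by it: a small loss of precision, with no inflation of type I error

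*Combined protocol and SAP*

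**What the plan says.** - Section 5.2 (Randomization): allocation is run centrally, with subjects "stratified by a) Sulfonylurea usage and b) whether they are on metformin alone or metformin plus one or 2 additional oral antidiabetic drugs at Screening".
- Section 8.3 (Primary Efficacy Evaluation): "subjects will be stratified by Screening HbA1C values and current treatment regimen". SU use is not named, and the treatment-regimen factor is not defined.
- Section 8.3.1: the ANCOVA is fitted "using baseline HbA1C and whether the subject is using additional antidiabetes drugs (beyond metformin) as covariates". The Synopsis (Statistical Methods) has the same model: "using baseline HbA1c and whether the subject is using additional antidiabetes drugs (beyond Metformin) as covariates".
- Section 4.1, criterion 4, limits background therapy: "Taking metformin only or metformin in addition to no more than two of the following: SU, DPP-4, SGLT-2, or TZD".
- Section 8.2.1 gives the planning values: "a drop in HbA1C of 0.6% is expected with a standard deviation of 1.2".
- Section 8.4 carries a similar method over to most secondary endpoints.

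**The concern.** Two things do not fit together.

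First, 5.2 and 8.3 describe different schemes. The treatment-regimen factor in 8.3 could be shorthand for the two drug factors in 5.2. Screening HbA1C cannot be read into 5.2 at all, so that is the firm conflict.

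Second, if 5.2 is right, the model leaves out one of the factors that constrained the randomisation. By criterion 4 every SU user is also an add-on user, so 5.2 gives three possible strata: metformin alone, add-on without SU, and add-on with SU. The add-on covariate separates only the first from the other two. SU against non-SU among add-on users is balanced by design but not modelled. Its variance inflates the model standard error although it barely affects the true sampling error of the treatment difference. The test is then mildly conservative and some power is given away. Leaving the strata unsettled also leaves the choice of covariates open later than it needs to be.

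**Working it through.** **The plan's own figure.** Section 8.2.1 gives a difference of 0.6, SD 1.2, 80% power and BID+TID against combined placebo (2:1). Sidedness is not stated; two-sided 5% reproduces the figure.

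- n(placebo) = (1 + 1/2) × (1.960 + 0.842)² × (1.2/0.6)² = 1.5 × 7.85 × 4 = 47.1, rounded up to 48. At 48 against 96 the power is 80.7%.
- 240 × 0.8 = 192 completers, and 192/4 = 48. The stated numbers hold and do not depend on the SU term.
- TID alone against placebo, the first test in Section 8.1, has 68.8% power at 48 per group. Both comparisons are therefore shown below.

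**Variance left in the residual.** Let q be the share on metformin alone, s the SU share among add-on users, and b the SU effect on HbA1C change after baseline HbA1C and add-on status. None of the three is in the documents; all are assumed.

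- Unmodelled variance V = (1 − q) × s × (1 − s) × b².
- Excess in the model SE = 1/√(1 − V/1.44) − 1, where 1.44 = 1.2².
- Equivalent completers = 192 × V/1.44.

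With q = 0.30 and s = 0.50, V = 0.175 × b²:

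| b | V | V/1.44 | SE excess | Completers |
|---|---|---|---|---|
| 0.2 | 0.007 | 0.5% | 0.2% | 0.9 |
| 0.4 | 0.028 | 1.9% | 1.0% | 3.7 |
| 0.6 | 0.063 | 4.4% | 2.3% | 8.4 |
| 0.8 | 0.112 | 7.8% | 4.1% | 14.9 |

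For q of 20–50% and s of 30–70%, the SE excess is 0.15–0.28%, 0.6–1.1%, 1.3–2.6% and 2.4–4.8% at the four effects.

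**Simulation under the 5.2 strata.** 192 completers, four arms, blocks of 12 within the three strata, same q and s, two-sided 5%; 10,000 null runs and 6,000 runs with a drug effect of 0.6. Paired entries are without/with the SU term.

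| b | Mean model SE, TID vs placebo | Power TID (%) | Power BID+TID (%) | Type I without term, TID; BID+TID (%) |
|---|---|---|---|---|
| 0.2 | 0.2454/0.2448 | 67.1/67.1 | 79.3/79.5 | 4.9; 5.2 |
| 0.4 | 0.2455/0.2430 | 67.9/68.5 | 80.4/81.2 | 5.0; 5.0 |
| 0.6 | 0.2456/0.2401 | 68.6/70.2 | 80.7/82.0 | 4.4; 4.7 |
| 0.8 | 0.2456/0.2356 | 69.0/71.7 | 81.2/83.1 | 3.9; 4.1 |

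Monte Carlo error on the type I rates is about 0.2 points.

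**With dropout.** A further simulation randomised 240 and dropped 20% (6,000 runs). At b = 0.8, type I error without the term was 4.0% (TID) and 3.9% (BID+TID), against 4.8% and 4.4% with it. Power rose from 66.9% to 69.9% and from 80.8% to 83.1%. At b = 0.4, type I error was 5.0–5.2% either way and power moved by 0.3 to 1.0 points.

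**If 8.3 is the scheme.** With SU not stratified, type I error without the term was 4.6–5.2% for b of 0.4 to 0.8. Adding SU gained 0.3 to 2.7 power points. The test is then nominal and only precision is lost. Continuous baseline HbA1C already covers most of a Screening HbA1C stratum.

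**Widest range tried.** In closed form, with add-on share 0.5–0.9, s 0.3–0.7 and b 0.2–0.8, adding the term gains 0.1–3.6 points for TID and 0.1–2.6 for BID+TID.

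**The case against.** The best case against is that this is very small. Section 4.1 requires stable oral therapy for at least 3 months before Screening, so much of any SU effect should already sit in baseline HbA1C, which is a covariate. That makes b = 0.2 at least as plausible as 0.6, which would equal the drug effect the trial is powered for. At 0.2 the power gain is 0 to 0.2 points. Conservatism becomes visible only from about 0.6, and only if 5.2 is the scheme used. The add-on covariate already covers one of the two factors in 5.2. Section 8 leaves further detail to a statistical analysis plan, which could add the term; no separate SAP text is in the document reviewed. The main simulation ignores dropout, multiple imputation and Cohort B, and uses the 240 randomised of Section 8.2.1, whereas 5.2 gives 265 for Cohort A.

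The points on size and conditionality stand, and the conclusion is limited accordingly. The rest does not remove the gap. Section 8.3.1 lists its covariates explicitly, and a later SAP would not cure a conflict between two protocol sections. The run with dropout gives similar results, and the percentage excess in the SE does not depend on the number randomised.

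**Conclusion.** The point holds. The strata in 5.2 and 8.3 conflict, at least on Screening HbA1C, and the primary model has no SU term although 5.2 stratifies by SU use. The consequence is mild. Under the 5.2 scheme and the assumed shares, the model SE is 0.2% to 2.3% too large for SU effects of 0.2 to 0.6, worth about 1 to 8 of 192 completers and 0 to 1.6 power points. An extreme effect of 0.8 gives about 4% and 2 to 3 points. No scenario inflates type I error, and the sample size is unaffected. The test is measurably conservative only if 5.2 was implemented and the SU effect is sizeable. The sizes rest on assumed SU prevalence and effect; no secondary endpoint was calculated. The correction is worth making because it is almost free, not because the present analysis is invalid.

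**What to change.** 1. State one set of strata in 5.2 and 8.3, matching what the IWRS implements. Define the treatment-regimen factor or delete it, and say whether the add-on factor has two levels or three (alone, plus one, plus two).
2. Put every stratification factor actually used into the primary ANCOVA alongside continuous baseline HbA1C. If 5.2 is right, that means SU use (yes/no) and metformin-alone status. Make the same change in the Synopsis.
3. Use the same terms in the multiple-imputation model (8.3.2) and in the secondary models under 8.4, so that all analyses match the design.
4. Settle this before unblinding.

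The cost is one degree of freedom (one more if the add-on factor has three levels) and two corrected sentences on the strata. The SU data are already collected for randomisation. The added term alone recovers the precision; it does not resolve the conflict between 5.2 and 8.3, so step 1 is needed as well.

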8.3.2 Handling of Missing or Spurious Data

The overall data will be analyzed using a multiple imputation method to account for missing or spurious data. Missing or spurious data will be imputed. Imputed values are drawn for a distribution (that can be different for each missing entry). This step results in *m* complete data sets. Each of the *m* completed data sets will be analyzed. This step results in *m* analyses. The results for the *m* analyses will be pooled into a final result. The details of how the missing or spurious values were imputed will be documented.

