8 STATISTICAL METHODS

This section describes the statistical methods to be used for the analysis and reporting of data collected under Protocol No. ORA-D-015. Additional details will be provided in the statistical analysis plan.

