8.6.8 Handling of Missing, Unused, or Spurious Data

Descriptive statistics and listings will be provided for all data. No substitution of missing data will be used in any calculations. Data points that appear to be spurious will be investigated and will not be excluded from the listings. Influential cases will be handled in an appropriate statistical manner.

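### The primary analysis imputes HbA1C values judged spurious as well as missing ones, and nothing supplied ties that judgement to an objective criterion or a blinded decision before lock

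*Combined protocol and SAP*

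**What the plan says.** Section 8.3.2 sits under the primary efficacy evaluation. It says "The overall data will be analyzed using a multiple imputation method to account for missing or spurious data", and then "Missing or spurious data will be imputed". The imputation model is left open: "Imputed values are drawn for a distribution (that can be different for each missing entry". On record keeping it says "The details of how the missing or spurious values were imputed will be documented".

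The rule feeds the primary test in Section 8.3.1: "Mean change from baseline to Week 12 HbA1C (Visit 9 value – Visit 3 value) will be tested using an analysis of covariance (ANCOVA) model". Section 8.4 analyses most secondary glycaemic endpoints by a similar method, so the rule may reach fasting glucose, the meal test and CGM. Weight is expressly exempt from imputation.

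The introduction to Section 8 promises generally that "Additional details will be provided in the statistical analysis plan". The supplied document has no separate SAP text.

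Section 8.6.8, on safety data, is worded differently: "No substitution of missing data will be used in any calculations" and "Data points that appear to be spurious will be investigated and will not be excluded from the listings". Its last sentence leaves influential cases to whatever handling is statistically appropriate.

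**The concern.** The sentence in Section 8.3.2 is an instruction. It puts recorded values called spurious in the same class as values never obtained. The supplied text does not define the term, name who decides, require the decision to be blinded or made before lock, or ask for an analysis with the observed values kept. The promised documentation covers how values were imputed, not why a value was rejected.

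There is little need for such a rule on this endpoint. HbA1C is measured by a central laboratory (Sections 6.1.5 and 6.1.5.4), results are imported electronically, and a query process exists to correct errors (Section 9.1.1).

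At stake is the primary estimate. If values are set aside because they look extreme, the estimate can be distorted even when everyone acts in good faith under the blind.

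**Working it through.** **The plan's own figure.** Inputs from Section 8.2.1: difference 0.6, SD 1.2, power 80%, BID and TID combined against combined placebo (2:1), 20% dropout. Alpha is 0.05 (Section 8.1), taken as two-sided.

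- Placebo n = (1 + 1/2) × (1.960 + 0.842)² × 1.2² / 0.6² = 1.5 × 7.85 × 4 = 47.1, so 48. This reproduces the plan.
- Power at 48 v 96 = Φ(0.6 / [1.2 × √(1/48 + 1/96)] − 1.960) = Φ(2.828 − 1.960) = 80.7%.
- Randomized: 192 / 0.80 = 240, as stated.

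The point changes none of these figures. The illustrations below use one active arm against placebo, 48 v 48 (96 values), as in the stepwise tests of Section 8.1. Baseline power there is Φ(0.6 / [1.2 × √(2/48)] − 1.960) = Φ(2.449 − 1.960) = 68.8% by the normal formula, and about 68% with the t distribution.

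**Assumptions for the illustrations (not from the documents).** Changes are normal with SD 1.2. Removed values are treated as missing at random, with the remaining values analysed as a stand-in for multiple imputation. Each setting had 20,000 to 40,000 simulated trials. The numbers of values removed are assumed, because the documents give no expected frequency.

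**Case 1: blinded removal.** The k values furthest from the pooled mean of all 96 are removed, whatever their arm.

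| Removed, of 96 | Type I error, no effect | Mean estimate, true 0.6 | Power | 95% coverage, true 0.6 |
|---|---|---|---|---|
| 0 | 5.1% | 0.60 | 68% | 95% |
| 2 | 4.8% | 0.53 | 62% | 94% |
| 4 | 4.7% | 0.49 | 57% | 92% |
| 6 | 5.0% | 0.45 | 53% | 89% |

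When the drug works, the largest falls are mostly in the active arm and the largest rises mostly in placebo. Removing both tails therefore pulls the arms together. The loss is 0.07, 0.11 or 0.15 points, or about 12%, 18% or 25% of 0.6. Multiple imputation with Rubin's rules gave the same estimates and type I errors of 5.2%, 5.2% and 5.5% for 2, 4 and 6 removed.

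**Case 2: selective removal, no true effect.** The k least favourable of 48 active-arm values are removed.

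| Removed, of 48 | Shift in difference | False wins for active |
|---|---|---|
| 0 | 0 | 2.4% |
| 1 | −0.06 | 4.6% |
| 2 | −0.11 | 7.0% |
| 3 | −0.15 | 9.9% |

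Proper multiple imputation (10 imputations, 4,000 runs) gave 2.1%, 4.8%, 6.8% and 10.3%.

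**The case against.** **Spurious means not genuine.** A mislabelled sample or failed assay is properly treated as missing, and Section 8.3.2 does not say that outliers are imputed. This is fair, and the fix keeps that practice. But Section 8.6.8 applies the word to points that only appear spurious, so the protocol's own usage does not confine it to proven invalidity.

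**The SAP may settle it.** It may, so a reader should not infer that documentation can come only after the fact. The wording of the documentation sentence is thin evidence of that, and Section 8 defers details generally. Still, the supplied text contains no criterion, and the deferral does not mention this issue. Section 3.7, by contrast, sends post-rescue data to the SAP by name.

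**The safety section contradicts the efficacy rule.** A reader might infer this, but the texts do not support it. Section 8.6.8 promises only that such values stay in the listings; a listed value can still be replaced in an analysis. Influential cases are left open there too.

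**Blinding and data controls make abuse unlikely.** Treatment is double-blind. The open regimen does not reveal the arm, because each Cohort A regimen includes placebo at 1:3 (Section 5.2). Changes after lock need joint written agreement (Section 9.2). These points stand, and they make Case 2 remote. They do not remove Case 1, which occurs under the blind. Nor do they tie the judgement to blinded review: the critical-variable review in Section 9.2 names safety and secondary data, not the primary endpoint.

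**Conclusion.** The point holds as a defect in a stated rule for the primary analysis, and it should be fixed. As written, the rule lets an observed HbA1C be replaced on a judgement that no supplied text makes objective or blinded.

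The realistic harm is attenuation: with a true effect of 0.6 and 2 to 6 of 96 extremes removed blind, the estimate falls to about 0.53 to 0.45, power falls by roughly 6 to 15 percentage points, and coverage falls to between 94% and 89%. This works against the drug. A reader might infer that blinded flagging inflates false positives or overstates precision in general. It does not when there is no effect, since type I error stays near 5%. Coverage suffers only when a true effect is attenuated.

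False-win rates of 5% to 10% are a worst case that needs arm-aware deletion. The documents give no sign that this is intended or likely. All sizes rest on the assumed numbers removed, normal data and SD 1.2. If few central-laboratory results are ever questioned, the practical effect will be small.

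**What to change.** In Section 8.3.2:

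- Impute only missing HbA1C values.
- Keep every observed central-laboratory HbA1C in the primary analysis unless the laboratory declares the sample or assay invalid before unblinding; treat such a result as missing.
- List all queried values before unblinding.
- Run one sensitivity analysis without the queried values.

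The cost is a short text change and one extra analysis. A few doubtful values that the laboratory has not invalidated will stay in the primary analysis. Sample size, visits and procedures do not change.
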